## 2 TRIAL OBJECTIVES AND ENDPOINTS

### 2.1 Objectives

#### Primary Objective

- To explore the safety and efficacy of TJ301 in patients with active ulcerative colitis.

#### Secondary Objectives

- To investigate the pharmacokinetics of TJ301 in patients with active ulcerative colitis.
- To investigate the pharmacodynamics of TJ301 in patients with active ulcerative colitis.
- To investigate immunogenicity of TJ301 in patients with active ulcerative colitis.

#### Exploratory Objectives

- To explore the relationship between pharmacokinetics and pharmacodynamics of TJ301 in patients with active ulcerative colitis.

### 2.2 Endpoints

#### Primary Endpoints

- Clinical and endoscopic remission at Week 12, defined as a full Mayo score  $\leq 2$ , no individual subscore  $> 1$ , rectal bleeding subscore = 0.
- Adverse events, vital signs, 12-lead Electrocardiography (ECG), and clinical safety laboratory abnormalities.

#### Secondary Endpoints

- Clinical and endoscopic response (decrease from Baseline in full Mayo score  $\geq 3$  and  $\geq 30\%$ , including decrease from Baseline in rectal bleeding subscore  $\geq 1$  or rectal bleeding subscore  $\leq 1$ ) at Week 12.
- Clinical remission at Weeks 4, 6, 8, 10, and 12 defined as a stool frequency subscore = 0, rectal bleeding subscore = 0, and 9-point partial Mayo score  $\leq 1$ .
- Clinical response (decrease from Baseline in 9-point partial Mayo score  $\geq 2$  and  $\geq 30\%$ , including decrease from Baseline in rectal bleeding subscore  $\geq 1$  or rectal bleeding subscore  $\leq 1$ ) at Weeks 4, 6, 8, 10, and 12.
- Mucosal healing defined as Mayo endoscopic subscore = 0 or 1 at Week 12.
- Change from Baseline to Weeks 4, 6, 8, 10, and 12 in 9-point partial Mayo score.
- Change from Baseline to Week 12 in full Mayo score.
- Change from Baseline to Week 12 in modified Mayo score (=full Mayo score excluding Physician's Global Assessment (PGA) subscore).

- Change from Baseline to Weeks 4, 6, 8, 10, and 12 in PGA score.
- FDA-defined remission at Week 12, defined as Stool frequency subscore=0, Rectal bleeding subscore=0, and Endoscopy subscore =0 or 1.
- Immunogenicity: Anti-TJ301 antibodies.
- PK subgroup:  $AUC_{inf}$ ,  $AUC_t$ ,  $\%AUC_{ext}$ ,  $C_{max}$ ,  $t_{max}$ ,  $CL$ ,  $V_z$ ,  $\lambda_z$ ,  $t_{1/2}$ , and MRT (if applicable).
- Peak and trough (pre-infusion) TJ301 serum concentration.

### **Exploratory Endpoints**

- Change from Baseline to Weeks 4, 8, and 12 in exploratory biomarkers (erythrocyte sedimentation rate [ESR], C-reactive protein (CRP), IL-6, IL-6/sIL-6R complex, neutrophil and platelet count, faecal calprotectin).

### 3 INVESTIGATIONAL PLAN

#### 3.1 Overall Trial Design

##### 3.1.1 Trial Design Diagrams

A schematic overview of trial design is shown in [Figure 2](#).

##### 3.1.2 Overall Design

This is a multicenter, stratified randomized, double-blind, placebo-controlled phase II study.

The trial includes a Run-in Period (if stable conventional treatment needed), a 4-week Screening Period, a 12-week double-blind Treatment Period, and a Safety Follow-up Period of 3 weeks to Day 105.

90 patients will be centrally, dynamically, randomly assigned to 3 groups (1:1:1) to receive 600mg TJ301 biweekly (Q2W), 300mg TJ301 Q2W or placebo Q2W. Randomisation will be stratified by prior corticosteroids treatment (yes/no) and consent to participate in PK substudy (yes/no). TJ301 or placebo administrations will occur on Days 0, 14, 28, 42, 56, and 70.

During the double-blind period and the follow-up period, patients should be on stable conventional treatment for UC.

There will be 9 ~ 10 main visits at the investigational site during the study:

- Visit 0: Run-in Period: at an optional visit (Visit 0), decision will be made if patients need stable conventional UC treatment to meet the following criteria: with corticosteroids stable for at least 2 weeks prior to Randomization at no more than 20 mg prednisone (or equivalent), and/or with medications containing 5-aminosalicylates (5-ASA) at no less than 2 g 5-ASA per day for at least 3 months and stable for at least 4 weeks prior to Randomization, and/or with azathioprine (AZA) at no less than 1.5 mg/kg/day or mercaptopurine (6-MP) at no less than 0.75 mg/kg/day for at least 6 months and stable for at least 6 weeks prior to Randomization. If patients already met the criteria, they will directly enter the Screening Period (Visit 1). If not, they will need stable conventional UC treatment during the Run-in Period except those who cannot tolerate the medications mentioned above.
- Visit 1: Screening Visit, start of Screening Period (Days -28 to -1 prior to Visit 2)
- Visit 2: Randomisation Visit (Baseline), start of 12-week Double-blind Treatment Period
- Visits 3-7: 5 visits during 12-week Double-blind Treatment Period
- Visit 8: End of Treatment (EoT) Visit, completion of 12-week Double-blind Treatment Period
- Visit 9: Safety Follow-up Visit, scheduled at 35 days after the last dose of IMP (Day 105).

Clinical assessments of disease activity will take place at Visit 1 (Screening Visit), Visit 2 (Randomisation Visit), Visit 3 (Week 2), Visit 4 (Week 4), Visit 5 (Week 6), Visit 6 (Week 8), Visit 7 (Week 10), and Visit 8 (Week 12). During Screening and at Visit 8 (Week 12), assessments of disease activity will also include endoscopy (colonoscopy or sigmoidoscopy); mucosal biopsies for assessment of mucosal healing, histology, immunohistochemistry will be collected during endoscopy at these time points.

TJ301 PK will be assessed in a subgroup of patients in Mainland China (24 patients, 8 per arm; electronically assigned at randomisation and consenting to the extra procedures). Blood samples for PK subgroup will be collected in as follows:

[figure not shown]
- At 1st dose: pre-dose and 0.5, 1, 2 (end of infusion), 6, 48, 144 (Day 6), and 240 (Day 10) h after the start of the 1st administration;
- At the 2nd, 3rd, 4th, and 5th administrations blood samples will be collected pre-dose and at the end of infusion;
- At 6th dose: pre-dose and 0.5, 1, 2 (end of infusion), 6, 48, 144 (Day 76), 240 (Day 80), 336 (Day 84), 480 (Day 90), and 840 h (Day 105) after the start of the 6th administration.

The actual sampling time will be recorded.

The schedule of blood sampling for PK assessment allows the evaluation of PK profiles after single dose and after multiple doses in patients with UC. Considering the terminal plasma half-life of 5.3 – 6.0 days for TJ301 in healthy volunteers, the last blood sample will be collected at 840 hours (5.8~6.6 half-lives of TJ301) after the last dose. Also due to the long half-life of TJ301, the scheduled sparse blood sampling would be able to capture the PK profile of TJ301.

In order to ensure that standard therapy is not withheld from patients not gaining sufficiently from IMP treatment, patients suffering a worsening in disease after Visit 5 are to be withdrawn. Worsening will be defined as an increase from last visit in Mayo rectal bleeding subscore  $\geq 1$ , over 3 consecutive days ([Appendix 1](#)). Such worsening should be evaluated by the Investigator and confirmed by endoscopy (no improvement or worse) prior to deciding whether or not to withdraw the patient.

For patients not completing the trial, a Safety Follow-up Visit will be scheduled 35 days (5.8 - 6.6 half-lives of TJ301) after the last dose of IMP. For patients completing the 12-week Treatment Period, likewise a Safety Follow-up Visit will be scheduled at 35 days after the last dose of IMP (Days 105).

**Figure 2 Overview of Trial Design**

### 3.1.3 Trial Schedule

First patient first visit is planned for Third Quarter 2017 and last patient last visit is planned for First Quarter 2020. The expected total duration of the trial is approximately 2.5 years.

### 3.2 Planned Number of Patients

In total, 90 patients with active UC at approximately 25-30 investigational sites globally will be enrolled competitively and randomised equally into three arms with TJ301 (two dose levels) or placebo.

### 3.3 Safety Review Committee

A Safety Review committee (SRC) will be established. The SRC is an expert advisory group commissioned and charged with the responsibility of evaluating, primarily, cumulative safety data at regular intervals. The SRC will review blinded data and provide recommendations to the Sponsor based on their evaluation.

During the conduct of the trial, the responsibilities of the SRC will be to periodically review safety data, evaluate any safety concerns, and make recommendations to the Sponsor regarding trial conduct and possible trial modifications. The SRC will comprise at least a medical monitor, a physician and a pharmacologist. All members have experience and expertise in their field of practice.

A SRC Working Procedure will be prepared and signed prior to enrolment of the first patient. The charter will outline the specific purpose and functions of the SRC-related to monitoring the safety of patients in the trial. This charter will also describe the procedures for data extraction and data delivery conventions to and from the SRC members for review purposes.

### 3.4 Discussion of Overall Trial Design

#### 3.4.1 Trial Design

This trial is designed as a randomised, double-blind, placebo-controlled proof-of-concept trial of TJ301. Patients will be on concomitant treatment with stable doses of corticosteroids, or immunomodulators, or 5-ASA/sulfasalazine – all first- or second-line standard of care in UC – for at least the duration of the 12-week Treatment Period (i.e. up to the primary endpoint). Two dose levels of TJ301 will be investigated, and as discussed in Section 3.4.4, modelling of the effect on a PD biomarker, based on PK measurements over a wide range of serum concentrations of TJ301, suggests that the chosen dosages may show a dose-dependent clinical efficacy.

The typical duration of induction treatment in active UC, both in clinical practice and in clinical trials, is at least 8 weeks. The novel mechanism of action with TJ301, with blockade of only IL-6 *trans*-signalling, may influence the time to a clinically relevant endpoint such as clinical remission. In order to capture the full extent of the potential treatment effect, the primary endpoint will be assessed at Week 12. As shown in the recent proof-of-concept trial with etrolizumab (10) in a

similar trial population as the one proposed with TJ301, placebo response was higher earlier during the treatment course (at Week 6 as opposed to Week 10). Thus, more substantive ‘true’ response and remission rates can be expected with longer treatment duration.

### 3.4.2 Selection of Endpoints

The prospectively defined primary efficacy endpoint will be a binary endpoint of clinical and endoscopic remission at Week 12, defined as a full Mayo score  $\leq 2$ , no individual subscore  $> 1$ , and rectal bleeding subscore = 0. The full Mayo score (range, 0-12; higher score is worse) is based on the clinician’s scoring of clinical signs and symptoms, as well as endoscopic scoring of gross colonic mucosal inflammation. While there is no validated scale for scoring the severity of inflammation or clinical symptoms in UC, the Mayo score has been extensively used in earlier clinical trials in UC, and shows a good correlation between the full Mayo score and the clinician-rated components only (partial Mayo score without endoscopy; see Section 7.1.1 for details). The partial Mayo score without endoscopy can be used to accurately predict inflammatory activity, and the evolution of a treatment effect even in the absence of endoscopy.

Nevertheless, the endoscopic component of the Mayo score allows a direct assessment of the inflammatory activity, which is suitable in a proof-of-concept setting. This should allow a more robust correlation between clinical efficacy outcomes, PK parameters, and PD effects.

### 3.4.3 Blinding

A central, computer-based randomisation procedure is used to eliminate selection bias. To reduce the risk of breaking the blind, IMP thawing and reconstitution will be carried out at the trial site by blinded site personnel, independent of the Investigator and the Sponsor. The appearance of the reconstituted IMP, as well as the infusion volume (290 mL) will be identical for all treatment groups.

In order to reduce bias as much as possible, the trial is double-blind, keeping all subjects and the investigator blinded to the treatment. The randomisation list will not be available to any person involved in the conduct and evaluation of the trial until the trial database is locked.

### 3.4.4 Selection of Doses in the Trial

The safety and tolerability of TJ301 have been investigated in phase 1, single- and multiple-ascending dose studies in both healthy subjects and patients with quiescent IBD (Crohn's disease) up to 750 mg without any concern. Pharmacokinetic results indicate dose proportionality in maximal concentration obtained ( $C_{max}$ ) and overall exposure (AUC) with a terminal half-life of approximately 4.7 days.

The doses and dose frequency selected for this trial are within a dose range that is considered safe and tolerable in healthy subjects and patients, trying to limit the number of i.v. infusion events.

[figure not shown]
Evidence from treatment with infliximab and etanercept indicate that a higher dose requirement in IBD compared to RA and psoriasis and may also vary between disease states. The low systemic

exposure in IBD can partly be explained by demographics of the patient population, development of antibodies to the drug and administration of concomitant immunomodulators, but could also be related to a disease state.

Lamina propria mononuclear cells obtained from surgical colon specimens from patients with Crohn's disease and UC showed that both CD4+ T-cells and macrophages produced increased amounts of IL-6 compared to controls (11). sIL-6R was found to be released via shedding from the surface of macrophages and mononuclear cells with increased production associated with elevated levels of IL-6. Mucosal T-cells from IBD patients have showed strong evidence for IL-6 *trans*-signalling with activation of STAT-3, and the anti-apoptotic factors bcl-2 and bcl-xl. Treatment with TJ301 is anticipated to induce apoptosis of disease-perpetuating T-cells (12), which are assumed to induce long-lasting secretion of matrix-degrading substances such as chemokines and matrix metalloproteinases, which promote transmural inflammation. The turnover of T-cells may influence the dosing frequency. Treatments of IBD patients normally employ a less frequent or lower dose, when clinical remission is achieved.

The activity of the drug has, in the phase 1 programme, been explored using an *ex vivo* assay measuring the level of activation (phosphorylation) of the second messenger STAT-3. The relationship between exposure (Figure 3a) and efficacy is not known. However, based on *ex vivo* experiments, target saturation resulting in a suppression of STAT-3 activation back to baseline levels is expected to occur above an exposure of 1 µg/mL. Thus, the dose levels for this trial were selected to test levels of exposure around the threshold.

The 75 mg dose every other week is, according to simulations, anticipated to suppress the second messenger signal to baseline level for a duration of at least one week and single dose data suggest approximately 80% occupancy after 14 days (Figure 3b). Both the 300 mg and 600 mg dose administered every other week are anticipated to suppress the activation of the IL-6/sIL-6R second messenger signal STAT-3 to baseline, as the trough levels are expected to be >1 µg/mL. The highest dose of 600 mg is selected to likely cover the highest anticipated dose in the therapeutic range of TJ301.

Blue line: 75 mg. Magenta line: 300 mg. Black line: 600 mg.

**Figure 3 a) Dose Proportional Pharmacokinetics of TJ301 and b) pSTAT-3/STAT 3 Ratio and Target Occupancy (TO) after Single Doses of TJ301**

This trial is to investigate the efficacy of TJ301 *versus* placebo added on top of standard of care, in the induction of response and remission in patients with active UC. The two doses selected are within the range of doses investigated in phase 1 with dose proportionality in systemic exposure, and with no evident safety signals. The two doses are selected to give exposure above (300 and 600 mg) full target saturation (expected at the theoretical threshold of 1 µg/mL at trough). The selected dose levels may enable elucidation of dose response.

### 3.4.5 Selection and Timing of Dose for Each Patient

During the 12-week Treatment Period, dosing will be infusions every 2 weeks, as administered by trial personnel at the trial site. Dosing is fixed-dose throughout the trial.

In the multiple dosing parts of the phase I study of TJ301, the maximum dose of TJ301 was set as 600 mg weekly for 4 consecutive weeks (4 doses totally). In this study, TJ301 will be administered at up to 600 mg every two weeks for 12 consecutive weeks (6 doses totally). The concentration-time curves from the phase I study indicated very limited accumulation of TJ301 in plasma after multiple dosing. Although there will be 2 more doses in this study compared with the phase I study, the averaged plasma concentration of TJ301 will be very similar between the two studies. Therefore the proposed maximum doses (600 mg Q2W) can be considered safe and tolerable in patients. In addition, usually it takes at least 8 weeks for the biologics targeting UC, such as infliximab, golimumab, etc., to induce remission in patients with UC. Thus a 12-week treatment period is

proposed for TJ301 in this study with the purpose that patients to be enrolled will be more likely to benefit from treatment.

### **3.4.6 Withdrawal Criteria**

In addition to the patient's right to withdraw from the trial at any time, as well as withdrawal at the Investigator's discretion as discussed in Section 4.4, the SRC (Section 3.3) will review blinded data, for safety.

In order to ensure that standard therapy is not withheld from patients not gaining sufficiently from IMP treatment, patients suffering a worsening in disease after Visit 5 are to be withdrawn. Worsening will be defined as an increase from last visit in Mayo rectal bleeding subscore  $\geq 1$ , over 3 days (Appendix 1). Such worsening should be evaluated by the Investigator and confirmed by endoscopy (no improvement or worse) prior to deciding whether or not to withdraw the patient.

### **3.4.7 Follow-up Procedures**

For patients completing the trial, a Safety Follow-up Visit will be scheduled on Day 105 (Week 15). For patients not completing the trial, a Safety Follow-up Visit will be scheduled 35 days (5.8 - 6.6 half-lives of TJ301) after the last dose of IMP. The procedures to be performed during the Safety Follow-up Visit are described in Section 6.3.

At the end of the trial patients will be treated for their UC at the discretion of the Investigator.

## 4 SELECTION OF TRIAL POPULATION

### 4.1 Trial Population

This trial is designed to include adult and elderly male and female outpatients with active, UC. Patients who fulfil all of the inclusion criteria (Section 4.1.1) and none of the exclusion criteria (Section 4.1.2) are eligible for inclusion in the trial.

#### 4.1.1 Inclusion Criteria

A subject will be eligible for inclusion in this study only if all of the following criteria apply:

1. Male and female patients 18-70 (inclusive) years of age.
2. Active UC confirmed by colonoscopy with biopsy or flexible sigmoidoscopy with biopsy at Screening, with extending > 15-cm past the anal verge from endoscopy.
3. Active UC with a full Mayo score  $\geq 5$  and a rectal bleeding subscore  $\geq 1$  at screening.
4. During Day -35 to Day-6 prior to Randomisation, an endoscopy subscore  $\geq 2$ .
5. Treated with conventional non-biological UC therapy: with corticosteroids stable for at least 2 weeks prior to Randomization at no more than 20 mg prednisone (or equivalent), and/or with medications containing 5-aminosalicylates (5-ASA) at no less than 2 g 5-ASA per day for at least 3 months and stable for at least 4 weeks prior to Randomization, and/or with azathioprine (AZA) at no less than 1.5 mg/kg/day or mercaptopurine (6-MP) at no less than 0.75 mg/kg/day for at least 6 months and stable for at least 6 weeks prior to Randomization.
6. A female subject has been sterilized or has been menopausal, or the subject has no pregnancy plan during the trial and voluntarily adopts effective contraceptive measures.
7. The patient is able and willing to comply with the requirements of this trial protocol.
8. The subject should be able to read and write to understand and fill out Patient Diary.
9. Voluntarily signed Informed Consent obtained before any trial-related procedures are performed.

#### 4.1.2 Exclusion Criteria

A subject will not be eligible for inclusion in this study if any of the following criteria apply:

1. Pregnant or breastfeeding women.
2. Contraindication to colonoscopy or sigmoidoscopy.
3. Allergies to any component of TJ301.
4. History of colostomy, colectomy or partial colectomy.
5. Current diagnosis of inflammatory bowel disease unclassified, Crohn's disease, ischemic colitis, fulminant colitis and/or toxic megacolon, patients with ulcerative colitis limited to the rectum (ulcerative proctitis), infective enteritis, amebic bowel disease and intestinal schistosomiasis.

6. History of malignancy other than a successfully treated non-metastatic cutaneous squamous cell or basal cell carcinoma and/or localized carcinoma *in situ* of the cervix. If the Screening colonoscopy shows evidence of dysplasia or a malignancy, the patient is not eligible.
7. Primary or secondary immunodeficiency including neutropenia (absolute neutrophil count <1500/ $\mu$ L); or lymphopenia (absolute lymphocyte count <500/ $\mu$ L).
8. Moderate to severe anaemia (haemoglobin <9 g/dL), or thrombocytopenia (platelet count <75,000/ $\mu$ L), or serum creatinine >2 mg/dL.
9. Autoimmune disease besides UC, with the exceptions of Sjogren's syndrome or hypothyroidism.
10. Clostridium (*C.*) *difficile* positive at screening visit or treated for *C. difficile* within the 4 weeks prior to Randomization.
11. Known clinically relevant chronic liver disease. Impaired hepatic function in the absence of a diagnosis of primary sclerosing cholangitis (serum transaminases >2.5 x upper limit of normal [ULN], alkaline phosphatase >2.5 x ULN, or abnormalities in synthetic liver function tests judged by the investigator to be clinically significant), or a diagnosis of primary sclerosing cholangitis, serum transaminases >3 x ULN, alkaline phosphatase >3 x ULN, or abnormalities in synthetic liver function tests (total bilirubin >1.5 x ULN) judged by the investigator to be clinically significant.
12. Serious underlying disease other than UC in the opinion of the investigator.
13. History of drug addiction within the last 1 year or current drug addiction or use of illicit drugs.
14. Any indication of the regular use of more than 40 grams of alcohol every day.
15. Smokers who smoke more than 10 cigarettes per day.
16. Known concurrent acute or chronic viral hepatitis B or C infection or human immunodeficiency virus (HIV) infection.
17. Presence or history of active tuberculosis (TB) or latent TB infection, defined as 1) a positive QuantiFERON-TB Gold test at Screening, or 2) a positive T-spot test within 4 weeks of Randomisation and evidence of current or previous pulmonary tuberculosis by chest X-ray within 12 weeks of Randomisation.
18. Positive immunoglobulin M antibody titres in the presence of negative immunoglobulin G titres to Epstein-Barr virus (EBV).
19. If clinical suspicion of cytomegalovirus (CMV), cytomegalovirus testing should be undertaken. Subjects with intestinal mucosa biopsy positive for cytomegalovirus at screening are to be excluded.
20. Receiving any investigational therapy or any approved therapy for investigational use within 30 days or 5 half-lives prior to Randomization (whichever is longer).
21. Currently taking any medications other than those allowed per protocol guidelines.

22. Infections (including diverticulitis) requiring treatment with antibiotics, antivirals, or antifungals within 14 days prior to Randomisation.
23. Any prior use of biologic drugs.
24. Received any live (attenuated) vaccines within 30 days prior to Randomisation.
25. Recent treatment with medium-to-high-dose intravenous corticosteroids (methylprednisolone 60 mg/day or hydrocortisone 300 mg/day) within 8 weeks prior to Randomisation or oral corticosteroids of more than 20 mg prednisone(or equivalent) within 30 days prior to Randomisation.
26. Receipt of cyclosporine, tacrolimus, sirolimus, or mycophenolate mofetil within 30 days prior to Randomisation.
27. Treatment with therapeutic enema or suppository, other than required for endoscopy preparation, within 14 days prior to the screening endoscopy and during the remainder of the trial.

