  17. Presence or history of active tuberculosis (TB) or latent TB infection, defined as 1) a positive QuantiFERON-TB Gold test at Screening, or 2) a positive T-spot test within 4 weeks of Randomisation and evidence of current or previous pulmonary tuberculosis by chest X-ray within 12 weeks of Randomisation.
  18. Positive immunoglobulin M antibody titres in the presence of negative immunoglobulin G titres to Epstein-Barr virus (EBV).
  19. If clinical suspicion of cytomegalovirus (CMV), cytomegalovirus testing should be undertaken. Subjects with intestinal mucosa biopsy positive for cytomegalovirus at screening are to be excluded.
  20. Receiving any investigational therapy or any approved therapy for investigational use within 30 days or 5 half-lives prior to Randomization (whichever is longer).
  21. Currently taking any medications other than those allowed per protocol guidelines.
  22. Infections (including diverticulitis) requiring treatment with antibiotics, antivirals, or antifungals within 14 days prior to Randomisation.
  23. Any prior use of biologic drugs.

24. Received any live (attenuated) vaccines within 30 days prior to Randomisation.
25. Recent treatment with medium-to-high-dose intravenous corticosteroids (methylprednisolone 60 mg/day or hydrocortisone 300 mg/day) within 8 weeks prior to Randomisation or oral corticosteroids of more than 20 mg prednisone (or equivalent) within 30 days prior to Randomisation.
26. Receipt of cyclosporine, tacrolimus, sirolimus, or mycophenolate mofetil within 30 days prior to Randomisation.
27. Treatment with therapeutic enema or suppository, other than required for endoscopy preparation, within 14 days prior to the screening endoscopy and during the remainder of the trial.

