### **7.1.4 Clinical Safety Laboratory Parameters**

Laboratory parameters: urinalysis (dipstick), urine pregnancy test, urine drug panel, haematology, clinical chemistry, coagulation, serum pregnancy test, TB, HIV, HBV, HCV, EBV, and CMV infection test, Clostridium difficile assay, erythrocyte sedimentation rate [ESR], C-reactive protein (CRP), neutrophil and platelet count, and biopsy samples ([Appendix 2](#)) will be measured at local sites according to the schedule in [Table 1](#).

Anti-TJ301 antibodies, Pharmacokinetics TJ 301, IL-6, IL-6/sIL-6R complex, and faecal calprotectin tests will be analysed in central lab; sample collection methods and handling procedures will be described in a separate laboratory manual.

The Investigator will review the laboratory results and evaluate and document whether the results are normal or abnormal and whether abnormal results are non-clinically significant or clinically significant. Pre-existing clinically significant conditions diagnosed as a result of the screening procedures must be recorded as medical history. If any clinically significant abnormal findings are discovered after informed consent or any pre-existing conditions worsen during the trial, these must be recorded as adverse events. The laboratory report will be signed and dated by the Investigator.

For female subjects, a serum  $\beta$ -HCG and a serum pregnancy test will be conducted at the Screening Visit (Visit 1) and urine pregnancy tests will be conducted at visit 8 and Follow-up visit.

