### **8.3 Adverse Events of Special Interest**

Adverse events of special interest include adverse events observed in earlier clinical development of TJ301 and those resulting from blocking IL-6 signaling shown by other drugs or investigational products.

Certain side effects were observed early on during the clinical development program for TJ301, including infusion-related reactions, headache, nasopharyngitis, myalgia, diarrhoea, cough, and decreased neutrophil count. In addition, certain side effects were characterized during the clinical development of other IL-6 inhibitors (e.g. tocilizumab) and have been shown to be mechanistically linked to its mode of action and its effect on inflammation. These side effects include neutropenia, thrombocytopenia, elevation of liver enzymes, lipid disorders (elevation of total cholesterol), severe infection (including tuberculosis), and gastrointestinal perforation.

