**Other Laboratory Assessments:**

- Urine screening for drugs of abuse (e.g. cocaine, barbiturates, amphetamines, opiates, benzodiazepine, and cannabinoids)
- HIV (HIV-1/2 Antigen and Antibodies)
- HBV (Hepatitis B Surface Antigen)
- HCV (Hepatitis C Antibody)
- TB (QuantiFERON-TB Gold; or T-spot test plus chest X-ray)
- EBV [Viral capsid antigen (VCA)-IgM test and VCA-IgG test]
- CMV (if applicable; CMV DNA load by real-time polymerase chain reaction assay)
- *Clostridium difficile* (*Clostridium difficile* toxin assay)
- Anti-TJ301 antibodies

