6.1, Table 1	Not applicable.	Add TB test at safety follow-up visit. Add Blood sampling for anti-TJ301 antibodies at Visit 3. Remove physical examination on V3, V5 and V7.	TJ301 may increase the risk for TB. An ADA sampling is added on Day14 (Visit 3). Physical examination every 4 weeks is sufficient.
6.1, Annotation a for Table 1	The screening endoscopy should be performed at Day -60 to Day -6 prior to Randomisation.	The screening endoscopy should be performed at Day -35 to Day -6 prior to Randomisation.	The endoscopy results obtained within 60 to 35 days prior to Randomisation may not be reliable as baseline. Some other footnotes for Time and Events Schedule have been updated.
6.2.3	Not applicable.	Add diary dispensing and diary review	Missed in V1.0.
7.1.1	Not applicable.	Note that the criteria of endoscopic appearance assessment in this study are DIFFERENT from the original criteria in (13). The Endoscopy subscore is modified so that a value of 1 does not	To emphasize that the criteria of endoscopic appearance assessment in this study is DIFFERENT from the original criteria of endoscopic

		include friability. Personnel responsible for endoscopic evaluation should NOT refer to the original criteria.	appearance assessment.
8.3	Not applicable.	
Adverse events of special interest include adverse events observed in earlier clinical development of TJ301 and those resulting from blocking IL-6 signaling shown by other drugs or investigational products.
 
Certain side effects were observed early on during the clinical development program for TJ301, including infusion-related reactions, headache, nasopharyngitis, myalgia, diarrhoea, cough, and decreased neutrophil count. In addition, certain side effects were characterized during the clinical development of other IL-6 inhibitors (e.g. tocilizumab) and have been shown to be mechanistically linked to its mode of action and its effect on inflammation. These side effects include neutropenia, thrombocytopenia, elevation of liver enzymes, lipid disorders (elevation of total cholesterol), severe infection (including tuberculosis), and gastrointestinal perforation.
	Adverse events observed for TJ301 and other IL-6 inhibitors can be regarded as adverse events of special interest.
8.5.2	
[name]
 
E-mail: [contact]
	
[name]
 
E-mail: [contact]
	CRO contact information is updated.

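### Exclusion criterion 17 excludes on a positive QuantiFERON alone but on a positive T-spot only with chest X-ray signs of pulmonary TB, so a T-spot-positive patient with a clear X-ray can be randomised

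*Protocol*

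**What the plan says.** Criterion 17 in Protocol Section 4.1.2 opens by excluding "Presence or history of active tuberculosis (TB) or latent TB infection". It then gives two numbered routes joined by 'or'.

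- Route 1 is a QuantiFERON result on its own: "latent TB infection, defined as 1) a positive QuantiFERON-TB Gold test at Screening".
- Route 2 is "a positive T-spot test within 4 weeks of Randomisation and evidence of current or previous pulmonary tuberculosis by chest X-ray", with the X-ray dated within 12 weeks of randomisation.

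The Synopsis carries the same criterion, including the requirement for "evidence of current or previous pulmonary tuberculosis by chest X-ray within 12 weeks of Randomisation". Appendix 2 (Other Laboratory Assessments) pairs the tests in the same way: "TB (QuantiFERON-TB Gold; or T-spot test plus chest X-ray".

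Table 1 and Section 6.2.2 call for a TB test at screening without naming one. Section 7.1.4 says that the listed laboratory parameters, TB among them, "will be measured at local sites according to the schedule in" Table 1. The trial is to run at 25-30 sites in Mainland China, Taiwan, the Republic of Korea and Australia. Nothing in the protocol says which site or patient gets which test.

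**The concern.** Latent TB is named as a reason for exclusion, and Appendix 4 gives the exclusion of such patients as the reason for the current wording. The T-spot route nevertheless asks for X-ray signs of current or previous pulmonary TB, so it cannot catch a latent infection that shows only as a positive blood test. The QuantiFERON route can. Eligibility of the same patient may then turn on the test used.

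What is at stake is patient safety and equal application of the entry criteria across sites. The sponsor treats TB as a relevant risk: Appendix 4 justifies the TB test at follow-up on the ground that "TJ301 may increase the risk for TB". Criterion 5 also admits patients on corticosteroids and on azathioprine or mercaptopurine.

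**Working it through.** The protocol gives no figure to reproduce, so the check is one of logic.

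**1. The rule as written.** The numbering ties the X-ray to route 2 only, and the semicolon in Appendix 2 confirms it. Route 1 or route 2 applies when: QuantiFERON positive OR (T-spot positive AND X-ray positive).

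**2. Its outcomes, by the test used, for a patient with no history of active TB.**

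| Positive blood test | Clear X-ray | X-ray signs of pulmonary TB |
|---|---|---|
| QuantiFERON | excluded | excluded |
| T-spot | **not excluded** | excluded |

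The two tests differ in one cell: positive blood test, clear X-ray.

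**3. Do the opening words close that cell?** The phrase 'defined as' can be read in two ways. If it governs latent TB only, active TB, present or past, is a separate ground, but this patient has none. If it governs active and latent TB together, the two routes are the whole definition and the patient meets neither. The patient is eligible on both readings.

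**4. Does another provision close it?**

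- Criterion 12 (serious underlying disease) rests on the investigator's opinion.
- Criteria 21 and 22 (disallowed medication; infection needing antibiotic treatment within 14 days before randomisation) could catch a patient whose positive result led to treatment, but not an untreated one.
- Investigator withdrawal (Section 4.4) and the blinded Safety Review Committee (Section 3.3) act after entry.
- The follow-up TB test (Section 6.3) comes after all dosing.

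None makes a positive T-spot a ground for exclusion at entry.

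**5. What an admitted patient would receive.** These inputs come from Sections 3.1.2, 4.2.2 and 6.3.

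- Allocation is 1:1:1 with two TJ301 arms, so the chance of TJ301 is 2/3 = 66.7%, and 90 × 2/3 = 60 of the 90 planned patients receive it.
- Infusions fall on Days 0, 14, 28, 42, 56 and 70, which makes 6.
- The next scheduled TB test is on Day 105, and 105 − 70 = 35 days after the last dose.

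These figures hold for any randomised patient who completes dosing. They describe exposure and do not measure how common the problem is.

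**6. Number affected.** This would need the share of patients screened by T-spot without a positive QuantiFERON, and the proportion of those who are T-spot positive with a clear X-ray. The protocol gives neither. The lower bound is 0, reached if only QuantiFERON is used.

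**The case against.** The strongest reply is that the wording is deliberate. It is the same in the Synopsis, Section 4.1.2 and Appendix 2, and it was introduced on purpose in Version 1.1. By stating what latent TB is 'defined as', the criterion sets the trial's own operational definition, under which a T-spot-positive patient with a clear X-ray does not have latent TB. The protocol nowhere says that the two assays are interchangeable.

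Part of this stands. The sections do not contradict one another, and a reader should not infer a drafting slip between them. The documents also do not establish that a T-spot-positive patient with a clear X-ray is infected. But calling the rule an operational definition does not explain why a positive blood test suffices on one route and not on the other, and the protocol offers no reason.

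A second objection concerns the remedy. One might infer that the X-ray condition is redundant beside the opening words and can simply be deleted. The documents do not support that. The opening words name a condition, while the X-ray is a means of finding it, including in a patient with no recorded history. Chest X-ray appears as a TB screen only in criterion 17 and Appendix 2, and 'defined as' may cover active TB too. Deleting it could weaken screening. This objection stands, and the fix below keeps the X-ray.

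A reader might also infer that TJ301 has been seen to cause TB. Section 8.3 does not say so. It places tuberculosis among effects for which "certain side effects were characterized during the clinical development of other IL-6 inhibitors", separately from the effects observed with TJ301 itself.

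**Conclusion.** The asymmetry is real and should be corrected. With a positive blood test and a clear X-ray, a patient is excluded on QuantiFERON and eligible on T-spot, under a criterion meant to exclude latent TB and with no rule on which test is used. The conclusion rests on the text alone and holds under either reading of 'defined as'.

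Its size is unknown. It matters only if some patients are screened by T-spot without a positive QuantiFERON, and it is nil if all sites use QuantiFERON only. It would go too far to say that patients with latent TB will be enrolled, or in what number. The existing safeguards narrow the gap without closing it. Sample size, power, type I error and the primary analysis are not touched.

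**What to change.** Reword criterion 17 in Section 4.1.2 and in the Synopsis to this effect:

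*Active TB, now or in the past, including signs of current or earlier pulmonary TB on any chest X-ray within 12 weeks of randomisation; or latent TB infection, meaning a positive QuantiFERON-TB Gold at screening or a positive T-spot within 4 weeks of randomisation.*

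Align the TB line in Appendix 2, so that the X-ray stays as a ground of its own and is no longer a condition for excluding a T-spot-positive patient.

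The cost is an edit in three places. No new test is required. The downside is some additional screening failures at sites that use T-spot; their number cannot be estimated from the protocol.
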